## **V. Study Design**

**a. Research design:** This study is comprised of an intervention arm (Group 1) and non-intervention arm (Group 2). For eligible women with low serum levels of vitamin D, we propose an 8 week open label, single arm “proof of concept” study to address concerns regarding vitamin D3 dosing, to monitor important laboratory parameters and to assess potential effects on short-term outcomes. While a randomized controlled trial (RCT) has been the traditional model to evaluate the efficacy of vitamin D supplementation, this design may be considered premature until the safety of this therapy has been evaluated in a patient population with the potential for high clinical acuity. For the women who meet all eligibility criteria except they have normal serum levels of vitamin D (Group 2), we will assess their symptomology and test associations with the biomarkers of inflammation.

**b. Study population:** Adult females with ER+ MBC can participate in the present study provided they are under the care of medical oncologist and meet all eligibility criteria. Women with early stage disease (Stages 0-3) or women with MBC who are ER- are unable to participate in this study.

**c. Sample size and power considerations:** Because this is a pilot project that will assess the feasibility, preliminary safety and short-term efficacy of a vitamin D3 intervention in this population, typical sample size calculations will not be employed. We will assess symptoms at baseline for all participants to establish prevalence estimates and at three time points in the intervention group to help increase our abilities to detect changes over time. Because of the high prevalence of vitamin D deficiency among breast cancer survivors (~75%) and the high volume of patients seen at LUMC and by [name] (collaborator), we anticipate that we can successfully recruit and enroll 50 women who meet the eligibility criteria. Our goal is to recruit 25 women for the intervention arm. Factoring in an attrition rate of ~20%, we should have complete data on 20 women who complete the intervention. This sample size is sufficient to demonstrate feasibility and will allow for the generation of effect size and variance estimates, as well as confidence interval widths around these estimates for future applications.

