**iii. Initial screening:** Referred participants will be phoned or seen in clinic to describe the study. If interested, age, health information and questions regarding vitamin D supplementation will be asked. If any of the exclusion criteria are reported, they will not be able to continue their participation. If initially eligible, they will be scheduled for a blood draw.

**iv. Baseline screening and enrollment:** Interested participants will be consented by the PI or study nurse in a private room, assigned a unique study identification number and undergo phlebotomy. Participants will have their blood drawn in the Cardinal Bernadin Cancer Center Phlebotomy Laboratory to determine serum levels of vitamin D and other relevant laboratory values (Refer to Measurements.) Participants will in the non-intervention arm (Group 2) will be asked to complete the questionnaires, either in person, over the phone or via mail.) The research study staff will review the results of the serum vitamin D blood tests and confer with the medical oncologist regarding further participation in the study. Participants who are vitamin D deficient (<30 mg/dl) will return to LUMC to participate in the intervention arm (Group 1), to complete questionnaires and to receive the study medication.

**Optional Biobanking.** At the study completion visit, participants may *optionally* agree to reposit up to two tablespoons of blood into CRO-BIOREP (LU# 204853) for future research purposes. Participants will sign a second informed consent document should they agree to reposit their blood. The research team members and Biorepository staff will each retain a copy of the signed repository informed consent document. It is important to point out that participants do not need to agree to reposit blood in order to participate in the trial.

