**x. Patient participation and compensation:** We anticipate that we can screen, recruit, and ultimately enroll 50 women over a 12 month time period (n=25 in Group 1, n=25 in Group 2) using patients at LUMC and those referred from RUMC. To enhance retention, participants will be scheduled on a day that is convenient for them and parking tokens will be provided to offset any costs of parking. Honorarium for data collection will be given in a graduated manner [\$20 baseline, \$30 follow up (Group1 only)]. To enhance medication compliance in the intervention arm, participants will be contacted weekly (phone call, text or email) and reminded to take their vitamin D supplements. For persons who drop out, we will assess the reason for study discontinuation and notify their medical oncologists regarding any recent laboratory findings, as appropriate.

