## **VII. Safety Monitoring Plan**

- a.** Published reports suggest that 50,000 IUs of vitamin D taken *daily* can increase vitamin D levels to more than 150 ng/dl and cause hypercalcemia. The proposed dosing for this study is 50,000 IUs per week, which equates to ~7,000 IUs/day. This dose has minimal side-effects in healthy populations, but may include bone pain, constipation, dry mouth, headache, stomach upset and loss of appetite. We will be monitoring laboratory values at baseline and 8 weeks, and patient symptoms at baseline, 4 and 8 weeks.
- i. Any patient who receives treatment on this protocol will be evaluable for toxicity. This study will utilize the CTCAE (NCI Common Terminology Criteria for Adverse Events) Version 4.0 available at (<http://ctep.cancer.gov>). Participants will be called after 4 weeks of supplementation to ascertain pill counts, gauge their general tolerance and capture symptom management data related to pain, fatigue, mood, sleep and overall health. Although toxicity and adverse side-effects from vitamin D3 supplement are rare, participants will be queried their general tolerance to the study medication during the 4 week phone call. The following criteria will be utilized to determine supplement suspension or supplement discontinuation: .If the participant develops Grade 1 toxicity that is felt to be possibly, probably, or definitely related to study supplement, the participant will continue to be monitored.
  - ii. If the participant develops Grade 2 toxicity that is felt to be possibly, probably, or definitely related to study supplement, the participant may go on study supplement holiday until toxicities are Grade 1 or lower (for no longer than 4 consecutive weeks).
  - iii. If a participant develops any Grade 3 or Grade 4 or has persistent Grade 2 toxicity beyond four consecutive weeks possibly, probably, or definitely related to the study supplement, the study supplement will be discontinued. A blood draw at the nearest Quest Diagnostics facility or the Cardinal Bernadin Cancer Center Phlebotomy Laboratory will be procured to obtain 25(OH)D and a comprehensive metabolic profile.

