  - iv. If a participant's serum calcium and corrected calcium\* exceeds 10.5 mg/dL, then study supplement will be suspended. The participant will be encouraged to lower any calcium intake and provided a handout on calcium sources. The serum calcium will be rechecked in two weeks and the participant may continue on study supplement if the serum calcium is below 10.5 mg/dL. Otherwise, the participant will be removed from study intervention. The participant may also be removed from study intervention for any Grade 2 or higher hypercalcemia (serum calcium > 11.5 mg/dl).  
\*Corrected calcium = serum calcium + [(4.0 – serum albumin) x 0.8]
  - v. In each of these cases, the follow up questionnaires and follow-up blood analyses will still be collected as per protocol eight weeks after the initial start of the intervention.
- b.** Participants may be re-challenged following a suspension. Specifically, participants who have had a study physician-ordered dose suspension may be re-challenged by returning to the full dosage, or

the study physician may decide to have the participant continue her participation on a reduced dose (e.g., 25,000 IUs/week) until study completion.

- c. A participant will be taken off study if she experiences any of the following adverse events: 1) hypercalcemia (>11.5 mg/dL), 2) a serum 25(OH)D level >100 mg/dL with normal calcium or symptoms of vitamin D indicating possible toxicity, 3) clinically significant increases in serum estradiol indicating a potential drug-nutrient interaction, or 4) has intolerable side-effects believed to be associated with vitamin D3 supplementation. Serious and/or unanticipated adverse events will be reported to the Loyola IRB within 24 hours of occurrence.
- d. To ensure the safety of participants, we will complete an exhaustive review of all safety measurements employed in this study after 7, 19, and 25 patients are enrolled. This includes examining their laboratory values, adverse event logs, and notifications in order to make a determination about whether the study should continue for all participants or whether the study should terminate.

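### Week-8 symptom change rests on the women who stay, because the protocol keeps questionnaires after stopping only for toxicity and calcium cases

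*Protocol*

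**What the plan says.** **Expected loss.** Protocol Section V.c: "Our goal is to recruit 25 women for the intervention arm", and then "Factoring in an attrition rate of ~20%, we should have complete data on 20 women who complete the intervention".

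**Women who stop for toxicity or calcium.** Section VII.a.v, after the toxicity and calcium rules: "In each of these cases, the follow up questionnaires and follow-up blood analyses will still be collected as per protocol", timed at eight weeks from the start.

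**Women who drop out.** Section VI.a.x: "For persons who drop out, we will assess the reason for study discontinuation and notify their medical oncologists regarding any recent laboratory findings". It mentions no outcome measure.

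**Women taken off study.** Section VII.c lists four grounds and says nothing about later questionnaires or bloods. Calcium above 11.5 mg/dL appears both there and in VII.a.iv, so one woman can fall under a rule that keeps her week-8 data and under another that is silent.

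**Remote collection.** The week-4 phone call (VII.a.i) is used to "capture symptom management data related to pain, fatigue, mood, sleep and overall health". Section VI.a.iv lets Group 2 answer questionnaires "either in person, over the phone or via mail".

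**Schedule (Table 1).** Pain, fatigue, mood, sleep and overall health are taken at weeks 0, 4 and 8. Handgrip and FACT-B/FACT-ES are taken at weeks 0 and 8 only.

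**Analysis.** Protocol Section VIII plans repeated measures over baseline, interim and follow-up. The SAP reports signed-rank tests of change from baseline in women treated for eight weeks. Neither gives a method for missing data.

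**The concern.** The protocol accepts the principle that outcomes should be collected after the supplement stops, but applies it to one group of leavers. A woman who withdraws because of progression, burden or lack of benefit comes under VI.a.x, where only her reason is recorded.

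In metastatic disease it is plausible that leavers fare worse than stayers. The investigators reason in a similar way in Section II.f: they say that not approaching sicker patients in their earlier pilot made quality of life look too high and symptoms too low. Losing sicker women after baseline could do the same to change scores.

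The stake is the Aim 2 estimate. Section V.c says that the study will supply effect sizes and variances for future applications, so an optimistic symptom change would carry into the next trial's sample size.

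**Working it through.** **1. The plan's own figure.** 25 × (1 − 0.20) = 20 with complete data, so about 5 without. This agrees with Section V.c. There is no power calculation to reproduce ("typical sample size calculations will not be employed").

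**2. Bias of the week-8 mean in stayers.** Let C and L be the mean changes in stayers and leavers, in SD of change, and delta = C − L. The mean for all treated women is (20C + 5L)/25, so the overstatement is C − (20C + 5L)/25 = (5/25) × delta = 0.20 × delta. The documents give no value for delta; the range below is assumed. The rejection rate is for a two-sided 5% t test on 20 women when the true mean change over all 25 is zero (noncentral t, standing in for the signed-rank test).

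| Assumed delta (SD) | Overstatement (SD) | Rejection rate |
|---|---|---|
| 0 | 0 | 5% |
| 0.25 | 0.05 | 5.5% |
| 0.5 | 0.10 | 7.1% |
| 1.0 | 0.20 | 13.6% |

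**3. Against random error.** The 95% half-width is t(0.975, n−1)/√n. At n = 20 it is 0.468 SD and at n = 25 it is 0.413 SD. The bias is smaller than this at every delta shown, but the interval makes no allowance for it.

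**4. Effect on a later trial (illustration).** Assume C = 0.5 SD. With delta 0.5, the all-treated mean is 0.5 − 0.10 = 0.40. With delta 1.0 it is 0.5 − 0.20 = 0.30. Required sample size goes as 1/effect², so a trial planned on 0.5 SD would need (0.5/0.40)² ≈ 1.6 or (0.5/0.30)² ≈ 2.8 times its planned number.

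**5. What recovery buys.** If k of the 5 leavers give scores and are typical of the 5, the remaining bias is delta × (5/25 − k/(20 + k)). For k = 3 this is delta × (0.200 − 0.130): 0.035 SD at delta 0.5 and 0.07 SD at delta 1.0. The half-width at n = 23 is 0.432 SD.

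**6. The split among the five is not given.** If some of them are VII.a.v cases who do return at week 8, only m women are missing and the factor is m/25. With m = 3 and delta 0.5 it is 0.12 × 0.5 = 0.06 SD. So 0.20 is the upper factor under the planned attrition.

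**The case against.** A reader might go further and infer that leavers contribute nothing after baseline, that no analysis could check the damage, and that improvement is overstated on every Aim 2 scale. The documents do not support this.

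- A woman who leaves after week 4 has a phone score in five symptom domains, and the Section VIII model can use it. The gap is week-8 values, plus all follow-up for women lost before week 4.
- Baseline scores, week-4 scores of late leavers and recorded reasons allow stayers and leavers to be compared and sensitivity analyses to be run, though these rest on assumptions.
- Delta is unknown and could be near zero. Eligibility asks for ECOG 0–2 and for unchanged treatment and/or clinical stability, and follow-up is only eight weeks.
- VI.a.x is silent on symptom scales; it does not rule them out. Nor does it say that the reason is obtained by phone. Terms for contact after withdrawal may stand in consent material not seen here.

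The remedy also has limits. Handgrip cannot be taken by phone, and FACT-B/FACT-ES are not scheduled at week 4. The full phone set is long: BPI 11 + FACT-BP 16 + Piper 22 + HADS 14 + PHQ8 8 + PSQI 19 + overall health 1 = 91 items. This is an uncontrolled, open-label pilot with symptoms as secondary endpoints.

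All of this stands and limits the point. It does not close the gap: no text extends VII.a.v to voluntary withdrawals or to VII.c, and a signed-rank test of week-8 change cannot use a woman without a week-8 score.

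**Conclusion.** The point holds in limited form. If the documents are followed as written, week-8 symptom change comes from women who stay, plus toxicity and calcium cases if the SAP's analysis set admits them. Read literally, the SAP would leave out women who stopped early even though VII.a.v collects their week-8 data.

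Under the planned 20% attrition, overstatement is likely if leavers do worse: up to 0.20 × delta, or 0 to 0.20 SD for delta from 0 to 1.0 SD. Delta is an assumption throughout. This is modest beside the 0.47 SD half-width, and Aim 1 safety conclusions do not turn on it. It is still worth correcting, because the estimates are meant to be carried forward and the route to better data already exists.

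**What to change.** **Protocol VI.a.x and VII.a.v.** Extend questionnaire collection to every Group 1 woman who leaves, for any reason, if she agrees. Offer the week-4 phone set (pain, fatigue, mood, sleep, overall health) at the discontinuation contact, with its date recorded, and again at week 8. Name a shorter subset in advance if burden is a concern. FACT-B/FACT-ES could be offered at week 8 by phone or mail, as questionnaires already are for Group 2. Handgrip will stay missing.

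**Protocol VII.c.** Reconcile it with VII.a.iv and VII.a.v on what follow-up data are collected from women taken off study.

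**Protocol VIII and SAP.** Make the primary Aim 2 symptom analysis a repeated-measures model on all treated women, using every available score at its actual time, so that a score at leaving is not treated as a week-8 score. State the missing-data assumption. Report the completer signed-rank result beside it, with the number of women behind each and the reasons for leaving.

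**Cost.** Some staff time and added burden on women who have chosen to leave; some will decline, so the bias is reduced rather than removed. The SAP is written in the past tense. If follow-up has closed, only the analysis and reporting changes remain open, and the extra collection is for the next trial.

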## **VII. Safety Monitoring Plan**

- a.** Published reports suggest that 50,000 IUs of vitamin D taken *daily* can increase vitamin D levels to more than 150 ng/dl and cause hypercalcemia. The proposed dosing for this study is 50,000 IUs per week, which equates to ~7,000 IUs/day. This dose has minimal side-effects in healthy populations, but may include bone pain, constipation, dry mouth, headache, stomach upset and loss of appetite. We will be monitoring laboratory values at baseline and 8 weeks, and patient symptoms at baseline, 4 and 8 weeks.
- i. Any patient who receives treatment on this protocol will be evaluable for toxicity. This study will utilize the CTCAE (NCI Common Terminology Criteria for Adverse Events) Version 4.0 available at (<http://ctep.cancer.gov>). Participants will be called after 4 weeks of supplementation to ascertain pill counts, gauge their general tolerance and capture symptom management data related to pain, fatigue, mood, sleep and overall health. Although toxicity and adverse side-effects from vitamin D3 supplement are rare, participants will be queried their general tolerance to the study medication during the 4 week phone call. The following criteria will be utilized to determine supplement suspension or supplement discontinuation: .If the participant develops Grade 1 toxicity that is felt to be possibly, probably, or definitely related to study supplement, the participant will continue to be monitored.
  - ii. If the participant develops Grade 2 toxicity that is felt to be possibly, probably, or definitely related to study supplement, the participant may go on study supplement holiday until toxicities are Grade 1 or lower (for no longer than 4 consecutive weeks).
  - iii. If a participant develops any Grade 3 or Grade 4 or has persistent Grade 2 toxicity beyond four consecutive weeks possibly, probably, or definitely related to the study supplement, the study supplement will be discontinued. A blood draw at the nearest Quest Diagnostics facility or the Cardinal Bernadin Cancer Center Phlebotomy Laboratory will be procured to obtain 25(OH)D and a comprehensive metabolic profile.
  - iv. If a participant's serum calcium and corrected calcium\* exceeds 10.5 mg/dL, then study supplement will be suspended. The participant will be encouraged to lower any calcium intake and provided a handout on calcium sources. The serum calcium will be rechecked in two weeks and the participant may continue on study supplement if the serum calcium is below 10.5 mg/dL. Otherwise, the participant will be removed from study intervention. The participant may also be removed from study intervention for any Grade 2 or higher hypercalcemia (serum calcium > 11.5 mg/dl).  
\*Corrected calcium = serum calcium + [(4.0 – serum albumin) x 0.8]
  - v. In each of these cases, the follow up questionnaires and follow-up blood analyses will still be collected as per protocol eight weeks after the initial start of the intervention.
- b.** Participants may be re-challenged following a suspension. Specifically, participants who have had a study physician-ordered dose suspension may be re-challenged by returning to the full dosage, or

the study physician may decide to have the participant continue her participation on a reduced dose (e.g., 25,000 IUs/week) until study completion.

- c. A participant will be taken off study if she experiences any of the following adverse events: 1) hypercalcemia (>11.5 mg/dL), 2) a serum 25(OH)D level >100 mg/dL with normal calcium or symptoms of vitamin D indicating possible toxicity, 3) clinically significant increases in serum estradiol indicating a potential drug-nutrient interaction, or 4) has intolerable side-effects believed to be associated with vitamin D3 supplementation. Serious and/or unanticipated adverse events will be reported to the Loyola IRB within 24 hours of occurrence.
- d. To ensure the safety of participants, we will complete an exhaustive review of all safety measurements employed in this study after 7, 19, and 25 patients are enrolled. This includes examining their laboratory values, adverse event logs, and notifications in order to make a determination about whether the study should continue for all participants or whether the study should terminate.

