### III. Study Aims

Several clinical trials are underway to investigate if vitamin D2 or D3 provided at various doses (10,000-50,000 IUs/week) can improve the side-effects associated with anti-estrogen therapies, specifically aromatase inhibitors (AIs). However, these current trials use variable forms of vitamin D and predominantly include women with Stage I-III disease, excluding women with metastatic breast cancer. Evaluation of the safety of vitamin D3 supplementation is crucial since supplementation can lead to hypercalcemia and importantly, *in vitro* studies have shown that vitamin D3 influences the transcription of a gene that increases estrogen production. To assure that vitamin D3 does not abrogate the clinical effects of anti-estrogen therapies, the effect of vitamin D3 supplementation on estrogen production requires evaluation. Therefore, the overarching goal of this pilot study is to evaluate the safety, feasibility and efficacy of vitamin D3 supplementation in women with MBC. We will address and test the following aims and hypotheses, respectively:

**Aim 1:** To determine if weekly supplementation of 50,000 IUs of vitamin D3 raises serum levels of 25(OH)D to >30 mg/dl without adverse effects.

**Hypothesis 1:** Women who are compliant with vitamin D3 supplementation, as evidenced by normalization (>30 mg/dl) or increases in their serum 25(OH)D levels, will not experience significant changes in serum calcium or serum estradiol levels.

**Aim 2:** To determine the effect of vitamin D3 supplementation on symptom management.

**Hypothesis 2:** Women who achieve serum concentrations of 25 (OH)D ≥30 mg/dl or experience significant increases in 25(OH)D will exhibit improvements in pain, fatigue, sleep, mood, muscle function and overall quality of life.

**Exploratory Aim:** To explore the mechanistic effects of serum vitamin D levels and vitamin D3 supplementation on inflammatory markers and potential associations with symptom management.

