**v. Study intervention:** Following the clinical practice guidelines of the Endocrine Society, participants in Group 1 will receive 50,000 IU of vitamin D3 once a week for 8 weeks. This dose of vitamin D3 is similar to those used in other breast cancer trials involving women with Stage 0-III disease, and should be sufficient to increase levels in normal weight, overweight and obese women within an 8 week time frame. In addition, weekly dosing will also help to increase study compliance and participants will receive a weekly reminder (phone call, email or text) to take their supplement. Because this is a single arm, open label trial, all participants will be aware that they are taking the study medication and that no placebo is being offered in this trial. Participants will be encouraged to take less than 1000 mg/d of calcium supplementation and to emphasize food sources of calcium (see calcium handout in the appendices). Participants in the non-intervention arm (Group 2) will complete all of the baseline (Week 0) study questionnaires and physical measures.

**vi. Study assessments and activities:** Guided by the Wilson and Cleary health-related QOL model, we will examine seven levels of patient outcomes, including: a) biological and physiological, b) symptom status, c) functional status, d) health perceptions, e) overall QOL, and f) characteristics of the individual and the environment. Variables, measures and times are delineated below (Table 1). Brief details about each of the measurement tools are described below.

Table 1. SAFE-D study variable, measures, constructs and timing				
	Variables	Measures	Wilson & Cleary construct	Week
Aim 1	Low vitamin D (Primary)	25(OH)D, calcium, , serum estradiol, CMP	Biological	0,8
Aim 2	General well-being (Secondary) Pain Fatigue Mood Muscle function Performance status Sleep Overall health QOL	Brief Pain Inventory, FACT-Bone pain Piper Fatigue Scale HADS, PHQ8 Hand grip strength ECOG PSQI Single item question FACT-B, FACT-ES	Symptom status Symptom status Symptom status Functional status Functional status Symptom status Health perceptions Overall QOL	0,4,8 0,4,8 0,4,8 0,8 0 0,4,8 0,4,8 0,8
	Serum vitamin d and Inflammation (Exploratory)	CRP, interleukins, TNF- $\alpha$	Biological	0,8

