Other Factors	Demographics and cancer history	Age, race, employment, home life, treatments	Individual, Physiological	0
	Diet	Calcium/Vit D & Fruit, vegetable, fiber screeners	Biological	0
	Obesity	Body composition, Anthropometrics	Physiological	0,8
	Physical activity	Godin	Physiological	0,8
	Support	MOS Social Support	Environmental	0,8
	Sunlight	Sun exposure tool	Physiological	0,8

**vii. Laboratory Outcomes:** Laboratory analyses will be conducted by the Core Laboratory of LUHS, within a Basic Science Laboratory at LUHS and/or by Quest Diagnostics. Serum vitamin D and serum

estradiol will be measured using liquid chromatography/tandem mass spectrometry (LC-MS/MS). This technique is considered the 'gold standard,' providing total 25(OH)D which includes vitamin D2 and vitamin D3, as well as total serum estradiol levels. Calcium will be quantified by spectrophotometry. Biomarkers of inflammation (e.g., C-reactive protein (high sensitivity), interleukins, TNF- $\alpha$ ) will be measured at baseline and follow up with the laboratory analyses conducted in batch to decrease intra-assay variability. The comprehensive metabolic panel (CMP) will be completed to assess baseline organ function, and includes albumin, alkaline phosphatase, ALT, AST, calcium, CO2, BUN/Creatinine, chloride, creatinine with estimated GFR, globulin (calculated), glucose, urea nitrogen, potassium, sodium, total bilirubin, and total protein.

**viii. General well-being outcomes:** To increase comparability across studies, the selected tools have been used previously in breast cancer and/or other cancer populations. (Copies of the tools can be found in the Appendices.)

*Demographics and treatment:* Similar to our previous study, we will obtain information on age, race/ethnicity, employment status, living situation, diagnosis, treatments (medical, surgical and radiation) and metastatic sites.

*Brief Pain Inventory-Short Form:* This validated instrument was designed to assess pain in cancer patients. It includes four items measuring the severity of pain in the last 24 hours on a scale of 0–10, plus seven additional items measuring the extent to which pain interferes with life activities.

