*Sun exposure:* Because sunlight constitutes the major source of vitamin D, the adult sun habits questionnaire by Glanz et al will be used. Two questions inquiring about summer sun exposure will be used quantify time spent in the sun, which directly correlates with serum vitamin D levels.

*Godin Exercise Leisure-time Questionnaire:* This 4-item tool allows for the quick quantification of time spent engaged in strenuous, moderate or light activities over a typical 7-day period showing reliability coefficients of 0.8 with  $\dot{V}O_2$  measures. A weekly leisure activity score is generated, as well as the frequency of leisurely activities. This tool is recommended and made available by the NCI.

*Medical Outcomes Study Social Support Survey:* The self-administered survey is a 19-item multi-dimensional scale assessing four aspects of social support: tangible support, affectionate, positive social interaction and emotional/informational support (Cronbach’s alphas >0.9 for all subscales.) Total and subscale scores are obtained and compared, with higher scores indicating more support.

**ix. Study completion:** Participants in the intervention will return to LUMC after 8 weeks of supplementation for their final blood analyses (serum 25(OH)D, calcium, , serum estradiol, inflammatory markers), anthropometric and body composition evaluations, pill counts and questionnaire completion. An 8 week intervention was selected because: 1) this timeframe is consistent with the clinical practice guidelines of the Endocrine Society for vitamin D repletion, and 2) it is an efficient and opportune time to assess the effects of vitamin D on biological and symptom outcomes. Participants in the non-intervention arm will not be followed after their baseline visit. They will be considered “complete” after their baseline visit.

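### The blood draw taken when the supplement is stopped for toxicity omits estradiol, so an early stopper's only planned post-baseline estradiol is an off-supplement value at week 8

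*Protocol*

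**What the plan says.** Protocol section III (Study Aims) gives two reasons for evaluating safety: hypercalcemia, and laboratory evidence that vitamin D3 acts on a gene that raises estrogen production. On the second it says that "the effect of vitamin D 3 supplementation on estrogen production requires evaluation". Hypothesis 1 names serum calcium and serum estradiol as the values that should not change significantly. Section VII, item c, lists "clinically significant increases in serum estradiol indicating a potential drug-nutrient interaction" among the events that take a woman off study.

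Table 1 (section VI.a.vi) gives the Aim 1 laboratory measures as "25(OH)D, calcium, , serum estradiol, CMP", at weeks 0 and 8. Estradiol is listed separately from the metabolic panel. Section VII.a confirms the timing: "We will be monitoring laboratory values at baseline and 8 weeks".

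Item a.iii of section VII adds one unscheduled draw, for women whose supplement is discontinued for related toxicity. It "will be procured to obtain 25(OH)D and a comprehensive metabolic profile". Item a.v then says that follow-up questionnaires and bloods "will still be collected as per protocol eight weeks after the initial start of the intervention". Section VI.a.ix includes estradiol in those bloods: "final blood analyses (serum 25(OH)D, calcium, , serum estradiol, inflammatory markers".

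**The concern.** The stop draw covers one of the two named safety concerns and leaves out the other. Calcium and albumin are in the metabolic panel, so hypercalcemia can be checked at the moment the supplement is withdrawn. Estradiol cannot. The next estradiol is tied to the calendar start of dosing, so the earlier a woman stops, the longer she has been off supplement when it is measured.

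What is at stake is the interpretability of estradiol in the women who tolerated the supplement worst. The protocol treats every treated woman as evaluable for toxicity, so they belong in the safety account. The abstract also plans to relate rises in 25(OH)D to changes in estradiol. The stop draw measures 25(OH)D without the estradiol that would pair with it.

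**Working it through.** **1. Is estradiol in the stop draw under another name?** Section VI.a.vii gives the panel's content: "The comprehensive metabolic panel (CMP) will be completed to assess baseline organ function, and includes albumin, alkaline phosphatase, ALT, AST, calcium", followed by electrolytes, renal function, glucose, bilirubin and proteins. Estradiol is not listed. I take the metabolic profile in a.iii to be this same panel.

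**2. Is there any other planned estradiol between weeks 0 and 8?** None. Table 1 and section VII.a give weeks 0 and 8 only. The week-4 contact is a phone call. The recheck in item a.iv covers serum calcium only.

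**3. How long after the last dose is the week-8 sample?** The inputs are weekly dosing for 8 weeks (section VI.a.v) and a final draw at week 8 from the start (a.v). If doses fall at weeks 0 to 7, a woman who takes k doses has her last at week k - 1, so the gap is 8 - (k - 1) = 9 - k weeks. If doses are counted at weeks 1 to 8, the gap is 8 - k weeks.

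| Doses taken (k) | Gap, doses at weeks 0-7 (weeks) | Gap, doses at weeks 1-8 (weeks) |
|---|---|---|
| 8 (completer) | 1 | 0 |
| 7 | 2 | 1 |
| 6 | 3 | 2 |
| 5 | 4 | 3 |
| 4 | 5 | 4 |
| 3 | 6 | 5 |
| 2 | 7 | 6 |
| 1 | 8 | 7 |

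An early permanent stop gives 2 to 8 weeks against 1 in completers, or 1 to 7 weeks against 0 on the other count. A late stop differs little from a completer.

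**4. What would a stop-draw estradiol add, by route?**

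- Grade 3-4 related toxicity: discontinuation follows directly, so the draw can be close to the last dose.
- Grade 2 lasting more than four weeks: item a.ii allows a supplement holiday. If the holiday began when the toxicity began, the stop draw is itself more than 4 weeks after the last dose. With the last dose at week 0, 1, 2 or 3, the draw falls after week 4, 5, 6 or 7, and the week-8 sample follows 8, 7, 6 or 5 weeks after the last dose. The gain is small. If there was no holiday, the draw can still be near exposure.
- Removal after a failed calcium recheck (a.iv): two weeks of suspension have already passed.

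**5. How many women?** The plan's only nearby figure reproduces: 25 x (1 - 0.20) = 20 completers. That 20% is general attrition, not a toxicity stop rate. No stop rate is given, and section VII calls toxicity rare. Assuming independent stops at a common rate r, the expected number is 25r and the chance of at least one is 1 - (1 - r)^25:

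| Assumed r | Expected stops of 25 | Chance of at least one |
|---|---|---|
| 2% | 0.5 | 0.40 |
| 5% | 1.25 | 0.72 |
| 10% | 2.5 | 0.93 |
| 20% | 5 | >0.99 |

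**The case against.** The a.iii draw is a work-up of suspected vitamin D toxicity, for which 25(OH)D, calcium, and renal and liver function are the natural tests. Leaving estradiol out contradicts nothing in the protocol. Item a.v still obtains a post-baseline estradiol from every woman stopped under item a, with a 25(OH)D at the same visit to show her exposure then. In a 25-woman pilot with no formal sample size calculation, the women concerned may number none or a few. All of this stands. It makes the point small in scope, but it does not turn the week-8 value into an on-treatment one.

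Three stronger readings are tempting, and the documents do not support them.

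- A reader might infer that off-supplement values dilute the estimated estradiol change. The SAP describes the change-from-baseline tests as made among women treated with 8 weeks of cholecalciferol. On its plain reading, early stoppers are outside that comparison. Protocol section VIII does not say how they are handled. Hypothesis 1 is also confined to compliant women, judged by their 25(OH)D.
- A reader might infer that criterion c.3 fails specifically in stoppers. With estradiol scheduled only at weeks 0 and 8, no planned test can trigger c.3 during dosing in any woman.
- A reader might infer that a rise would resolve unseen. The documents give no clearance time for 25(OH)D and no time course for an estradiol effect.

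**Conclusion.** The omission is plain in the text and worth correcting as a cheap improvement of small scope. For a woman stopped early under item a, the only planned post-baseline estradiol comes about 2 to 8 weeks after her last dose, against about 1 week in completers, assuming doses at weeks 0 to 7. What is established is that this value is not on treatment, not that it would miss anything.

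The clear benefit is confined to Grade 3-4 related stops. Where a holiday or suspension came first, a stop-draw estradiol may already be weeks off supplement and adds little. The number of women affected rests on assumed stop rates.

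The conclusion covers women stopped under item a. For women taken off study under item c, the text does not clearly say whether a.v applies.

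**What to change.** Add serum estradiol, by the LC-MS/MS method already specified in section VI.a.vii, to the a.iii draw. Record weeks since last dose with every such value, and do not label it as on-supplement, since after a holiday it may not be. Keep the week-8 sample as scheduled. In the safety report, list early stoppers' estradiol values separately, each with its weeks since last dose.

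The cost is one extra assay for each of the few women who stop, on a draw already required, with no added visit. No dose or stopping rule changes.

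The SAP is dated November 2018 and written in the past tense. If data collection is over, the reporting part still applies: identify any early stoppers and list their week-8 estradiol in the same way.
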